2.1.3 Evaluation of treatment effects on locally recurrent breast cancer

A proportion of patients with locally recurrent breast cancer have non-measurable disease. As long as we accrue only patients with locally recurrent breast cancer, we will include those who have only non-measurable local lesions. Defining the overall response rate in this population would be difficult; however, it is reasonable to define the rate of control for measurable and immeasurable disease with PFS and OS. In addition, some biological agents such as imatinib have cytostatic effects on gastrointestinal stromal tumor but lack tumor shrinkage properties; that is, although the size of tumors are similar, the agents induce tumor necrosis. The proposed study agent is expected to induce tumor necrosis and yield overall response rate and disease control rate that is a reasonable surrogate for its efficacy.

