8.2. Evaluation of distant metastases (before cycle 5)

If a patient has distant metastasis, every effort will be made to obtain tissues from an easily accessible metastatic site. If patient does not have distant metastasis or distant metastasis is not accessible, core biopsy of local lesions will be needed to collect tumor tissue. Every effort will be made to obtain biopsy tissue before cycle 5 for at least 60% of enrolled patients.

A pathologist collaborator will be notified before the biopsy and will handle the resected specimen. Every attempt will be made to identify any tumor change such as necrosis.

Hematoxylin and Eosin staining will be performed with formalin-fixed paraffin-embedded

blocks to determine tumor, and immunohistochemical (IHC) staining will be made for immunity assessment. IHC assays will include CD3, CD4, and CD8 for T-cell immunity assessment, CD20 for B-cell immunity assessment, and CD16, CD56, and Granzyme B for NK cell immunity assessment. Cleaved caspase 3 staining for an apoptosis assay, Ki67 for a proliferation assay, and HSV antigen staining will be performed. If the remaining sample is ample, CD45RO, TIA-1, FoxP3, CD25, OX-40, CD56, CD57, CD1a, CD208, myeloperoxidase, CD68, COX-2, MHC Class I, and MHC Class II will also be assessed in [name] laboratory at MD Anderson.

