9.0. Criteria for response, overall response and disease control

Response must be evaluated using RECIST ver.1.1. Tumor lesions must be accurately measured in at least one dimension (longest diameter in the plane of measurement is to be recorded) with a minimum size of 10 mm by CT scan (irrespective of scanner type) and magnetic resonance imaging (MRI) (*no less than double the slice thickness and a minimum of 10 mm*), 10 mm caliper measurement by clinical examination (when superficial), and 20 mm by chest X-ray (if clearly defined and surrounded by aerated lung).

Tumor lesions must be accurately measured in at least one dimension of local recurrence and skin metastases if applicable. These will be measured by caliper, and the extent of disease should be recorded on a photograph with a scale marker and injection marker. If these lesions are immeasurable, their extent should also be recorded on a photograph with a scale marker and injection marker to assess the rate of overall response.

9.1. Complete Response (CR): Disappearance of all target and non-target lesions at a minimum of 4 weeks.

9.2. Partial Response (PR): At least a 30% decrease in the sum of the longest diameter of the target lesions at a minimum of 4 weeks, taking as a reference the baseline sum of the longest diameter with target.

9.3. Stable Disease (SD): Neither sufficient shrinkage to qualify for PR nor sufficient increase to qualify for progressive disease (PD), taking as a reference the smallest sum of the longest diameter since the treatment started with target lesions.

9.4. Progressive disease (PD): At least a 20% increase in the sum of diameters of target lesions, taking as reference the smallest sum on study (this includes the baseline sum if that is the smallest on study). In addition to the relative increase of 20%, the sum must also demonstrate an absolute increase of at least 5 mm. (Note: the appearance of one or more new lesions is also considered progression). In the previous phase III melanoma study, PD (defined by modified WHO criteria) prior to response was observed in about 50% of responders, and median time to response was 4.1 months. Thus, for this study purpose, a true PD will be confirmed at the end of cycle 10 (approximately 5 months) as long as patients tolerated the treatment.

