13.0. Statistical consideration

13.1. Statistical design

The primary objective of this phase II trial is to assess the efficacy of talimogene laherparepvec as a single agent in locally recurrent IBC and non-IBC patients. The primary endpoint is the rate of overall response.

The overall response rate is defined as the percentage of CR, PR in overall patients. Patients will be evaluated for disease control at the end of cycle 4 (2 months), cycle 8 (4 months) and cycle 10 (5 months). If patients have measurable disease only and achieve CR or PR, they will be considered Response Type I. If patients have non-measurable disease only, and achieved CR, they will be considered as Response Type II. If patients have both measurable and non-measurable disease and achieve CR or PR at the measurable disease sites, and achieved CR at the non-measurable disease site, they will be considered as Response Type III. If patients have mixed responses such as progression of measurable disease and no progression of non-measurable disease at 5 months or vice versa, they will be considered to have uncontrolled disease. The Overall Response rate will be defined as a sum of the 3 response types.

The trial will be conducted using a two-stage design and the overall response rate will be estimated accordingly. It is assumed that the talimogene laherparepvec single agent will have a response rate of 20%. A response rate of 5% or lower will be considered treatment failure and the regimen will be rejected under this circumstance. 13 patients will be enrolled to the first stage. The study accrual will be delayed until all 13 patients are evaluable for response. A summary report will be submitted to the medical monitor in the IND office. If no patients achieve an overall response to the treatment, the trial will be stopped and the regimen will be declared as ineffective. If there are 1 or more patients achieve an overall response, 22 more patients will be enrolled to the study to reach a total of 35 treated patients. By the end of the study, the new regimen will be rejected if less than or equal to 3/35 patients achieve overall response and will not be considered worthy of further investigation otherwise.

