Secondary objectives includes determining the overall disease control rate, local overall response rate and disease control rate, PFS, and OS in all patients; the local overall response rate and disease control rate, PFS, and OS in patients without distant metastases; and the local overall response rate and disease control rate, PFS, and OS in patients with distant metastases for defining the local efficacy of talimogene laherparepvec injection among breast cancer patients with inoperable local recurrence after surgery. In addition, this includes safety and tolerability of talimogene laherparepvec in these patients. The definition of PFS is time from treatment initiation until disease progression or death and this progression needs to be confirmed after the end of cycle 10. For example, patients who showed progress at 2 months but responded as PR at 5 months, we determine this as PR. In contrast, patients who showed progress at 2 months and was confirmed PD at 5 months, we determine this as PD at 2 months. The definition of OS is time from treatment initiation until any cause of death.

Analysis plan:

By the end of the study, the overall response rate will be estimated with 95% confidence intervals for all evaluable patients and for patients with or without distant metastasis, separately. PFS and OS from registration will also be estimated using Kaplan-Meier method with 95% confidence intervals.

Biomarker endpoints will be measured in tissue and in surrogate blood or plasma before and after the treatment. Correlation between biomarkers from various markers and between tissue and blood/plasma will be assessed by Pearson or Spearman rank correlation coefficients for

continuous biomarkers and by chi-square or Fisher's exact test for discrete covariates. The associations between markers or change in the level of markers and overall response status will first be assessed graphically and then tested using a t-test/analysis of variance or Wilcoxon rank sum test/Kruskal-Wallis test, when appropriate. Repeated measures analysis including mixed effects modeling will be performed to analyze biomarkers change over time. We may also evaluate the association between the changes in the level of marker and the overall response status.

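### Immune markers are tested against clinical effect only through CR/PR status, about 7 against 28 patients at the design rate; an ordered-response test on data already recorded would have roughly 9 to 20 points more power

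*Combined protocol and SAP*

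**What the plan says.** The Analysis plan in section 13.1 states: "The associations between markers or change in the level of markers and overall response status will first be assessed graphically and then tested using a" t-test or analysis of variance, or the rank-based equivalents, as appropriate. A later sentence in the same paragraph again names overall response status as the outcome for marker change. The remaining marker analyses are correlations among markers and between tissue and blood, and mixed models of marker change over time. None of them uses tumour size or response grade.

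Sections 9.5 and 13.1 define overall response as CR or PR, or CR alone where disease is non-measurable. Finer data are collected. Section 9.0 says of local and skin lesions that "These will be measured by caliper, and the extent of disease should be recorded on a photograph with a scale marker and injection marker". Sections 9.1 to 9.4 grade each patient CR, PR, SD or PD from the sum of longest diameters, and disease control, which depends on SD, is a secondary endpoint (13.3).

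On numbers, section 13.1 says "It is assumed that the talimogene laherparepvec single agent will have a response rate of 20" per cent and "A response rate of 5% or lower will be considered treatment failure". The first stage is 13 patients, and if at least one responds, "22 more patients will be enrolled to the study to reach a total of 35 treated patients". For on-treatment tissue, section 8.2 says "Every effort will be made to obtain biopsy tissue before cycle 5 for at least 60% of enrolled patients". No effect size, significance level or power is given for any marker analysis.

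**The concern.** Reducing a graded outcome to a responder split discards information, and an uneven split discards more. The split also treats a patient with lasting stable disease and one with rapid progression as the same. Yet section 2.1.3 expects possible activity without shrinkage, saying of cytostatic agents that "although the size of tumors are similar, the agents induce tumor necrosis".

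The protocol's own prior data show the risk. Sections 4.1 and 4.4.3 report that the phase 1 study, across tumour types, had no major responses: 8 of 30 patients were stable, 19 progressed and 3 were not evaluable. A status test on such data could not be run at all, whereas an ordered test could still compare 8 SD with 19 PD.

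At stake is how a null marker-response result can be read. With few responders it could mean either that there is no association or that the test had little chance of finding one.

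**Working it through.** **1. The plan's own figures.** Rule: stop at 0/13, reject at 3/35 or fewer.
- At 5%: early stop = 0.95^13 = 51.3% (plan: 51%); expected N = 13 + 22 × (1 − 0.513) = 23.7 (plan: 23.7); probability of claiming promise 8.44% (plan: 8.4%).
- At 20%: early stop 5.5% (plan: 5%), expected N 33.8 (plan: 33.8), probability of claiming promise 90.3% (plan: 90%).

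The design figures reproduce.

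**2. Group sizes at 20%.** Full sample: 0.20 × 35 = 7 responders against 28. Tissue before cycle 5 at the 60% minimum: 0.60 × 35 = 21 patients, and 0.20 × 21 ≈ 4 against 17.

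**3. Information lost by the cut.** Suppose marker and tumour change are bivariate normal. Cutting tumour change at its best 20% multiplies the correlation by φ(0.84)/√(0.2 × 0.8) = 0.280/0.400 = 0.70. Since 0.70² ≈ 0.49 and 0.49 × 35 ≈ 17, the 35 patients carry roughly the information of 17.

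**4. Power by simulation.** Assumptions, none from the plan: bivariate normality, correlation ρ, two-sided 5%, response = best 20% of tumour change, grades 5% CR, 15% PR, 30% SD, 50% PD. Results for n = 35:

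| ρ | t-test on status | Spearman, ordered grade | Gain | Spearman, percent change, all measured | Gain |
|---|---|---|---|---|---|
| 0.3 | 23% | 32% | 9 | 38% | 15 |
| 0.4 | 37% | 54% | 17 | 62% | 25 |
| 0.5 | 55% | 74% | 19 | 84% | 29 |
| 0.6 | 73% | 91% | 18 | 96% | 23 |

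For n = 21 at ρ = 0.5: t-test 34%, ordered 52%, percent change 59%.

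The ordered gain depends moderately on the assumed PD share. Against a rank test on status, for ρ from 0.3 to 0.6, it is 14 to 26 points with 30% PD and 9 to 18 points with 60% PD.

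**5. How fragile the percent-change gain is.**
- If 60% of patients are measurable (21 of 35), the gain over the status test in all 35 is about 2 to 12 points for ρ from 0.2 to 0.7. At ρ = 0.5, Spearman has 59% against 55%.
- If the worst 20% lack a fixed-time measurement, Spearman has about 51% against 55% at ρ = 0.5, so there is no gain.

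**6. The 5% rate under the two-stage rule.**
- Stop at 0/13: 51.3%.
- Continue and end with exactly 1/35 (one response among the first 13, none in the next 22): 13 × 0.05 × 0.95^34 = 11.4%.
- Fewer than 2 responders: 51.3 + 11.4 ≈ 63%.

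With no responder there is no status test. With one in 35, the smallest two-sided exact Wilcoxon p-value is 2/35 = 0.057, which cannot reach 5%, and a pooled t-test would rest on one patient's value.

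**The case against.** **The wording may already allow response grades.** Analysis of variance and Kruskal-Wallis admit more than two groups. But overall response is defined as CR/PR or not. Even on the generous reading, an unordered four-group test has only about 53 to 56% power at ρ = 0.5, against 74 to 76% for an ordered one. This does not rescue the plan.

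**Percent change is not a clean substitute.** This stands. Section 5.1.10 admits lesions from 5 mm, while section 9.0 requires 10 mm for measurement. Section 2.1.3 includes patients with only non-measurable lesions, and scans are done as clinically indicated. Under section 9.7, early deaths and losses count as failures in the intent-to-treat analysis, but they may have no later diameter sum. Percent change also omits new and non-target disease, and it would miss necrosis without shrinkage.

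**The simulation flatters the graded analyses**, because it makes response an exact cut of one variable. In the trial, response also depends on non-target lesions, new lesions, four-week persistence and cycle-10 confirmation. This stands as a caution on the sizes. It weighs less on the ordered analysis, whose grades already include those elements.

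**The correlative objectives do not rest on this test.** This largely stands. Section 1.3 asks about changes in blood and tissue markers, which the mixed models address. A reader might infer that a null association would make the whole correlative programme uninformative; the documents do not support that.

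**The tissue split is a lower bound.** This stands. The 60% is a minimum for biopsies before cycle 5. Baseline tissue is planned for all patients (section 7.2.13), so 4 against 17 does not apply to it.

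**Conclusion.** The point holds as an inexpensive improvement to an exploratory analysis. The documents alone establish that overall response status is the only clinical outcome used for markers, that about 7 of 35 patients are expected to respond at the design rate, and that the SD and PD grades go unused. The gain of roughly 9 to 20 points from an ordered test rests on an assumed correlation of 0.3 to 0.6, a two-sided 5% level and an assumed grade distribution. It should be quoted with those conditions.

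The documents do not support two stronger readings.
- A reader might infer a fixed cost of 10 to 30 points from not using percent change. That needs near-complete, fixed-time measurement, which the eligibility and scan rules do not ensure. The plausible gain runs from about zero to 29 points.
- A reader might take the low-response risk from 35 patients at a 5% rate, giving 0.95^35 + 35 × 0.05 × 0.95^34 = 47% with fewer than 2 responders. That ignores the stop at 0/13. The figure for this design is about 63%, and most of those trials end with 13 patients. Among trials that reach 35 it is 11.4/48.7 = 23%. At 13 patients no method does well: even complete percent-change data give about 38% power at ρ = 0.5.

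The primary conclusion is unaffected.

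**What to change.** In the Analysis plan of section 13.1:

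1. Add, as the main marker-efficacy analysis, an ordered-trend test (Spearman or Jonckheere-Terpstra) of each marker and each marker change against best overall response ordered PD<SD<PR<CR, in all patients with an assessed response. Grade patients by the plan's existing rules, including cycle-10 confirmation of progression.
2. Add, as supportive, the correlation of each marker with percent change from baseline in the sum of longest diameters at one named assessment, in patients with measurable disease. Report how many patients lack the value and why.
3. Keep the responder versus non-responder comparison.

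The cost is some wording and one or two more exploratory tests per marker, which adds to the multiplicity that any report should acknowledge. Percent change remains undefined for patients with only non-measurable disease and may be informatively missing after early death or dropout, which is why it should not be the main analysis. No new patients, visits or samples are needed. The primary endpoint, the response definition and the two-stage rule stay as they are.

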13.2 Primary endpoint

The rate of overall response for measurable and immeasurable disease in all patients.

13.3. Secondary endpoints

13.3.1. overall disease control rate, PFS, and OS in all patients

13.3.2. Local overall response rate and disease control rate, PFS, and OS in all patients.

13.3.3. Local overall response rate and disease control rate, PFS, and OS in patients without distant metastases.

13.3.4. Local overall response rate and disease control rate, PFS, and OS in patients with distant metastases.

15.0 Appendices

15.1 Sample Fax Cover Sheet for Individual Safety Reports (Amgen Global Safety)

Investigator Sponsored Study Amgen ISS <<LSO/SOPS - Select Category>> FAX Transmittal Form <<LSO/SOPS - Enter Product>>
 
<<LSO/SOPS - Enter Amgen Study Number>> / <<LSO/SOPS - Enter Sponsor Study ID, if applicable. If none, delete line>>
	
To: Amgen Global Safety, <<LSO/SOPS - Enter Location>>	AMGEN ISS PROTOCOL #: _____
Phone No: <<LSO/SOPS - enter Local Phone # or N/A for US>>	Sponsor: <<LSO/SOPS - Enter Institution Name>> Sponsor Contact Name: _____
Fax No: <<LSO - enter Local Fax # >> <<SOPS - select Fax #>>	Fax No: _____ Phone No: _____ Date: _____

Use this form as a cover page for an individual report, for batched individual reports, and for line listings. ***NOTE: Please use data reconciliation fax cover sheet to submit data reconciliation line listings.
	

Fax transmission contents (Check all that apply):
	

To be sent immediately after each single case submission to RA, EC, IRB or DMC:
	

 Expeditable Serious Adverse Events/Serious Adverse Drug Reactions # of Reports Submitted: _____
	

To be sent in regular intervals per contractual agreement (eg, as batched individual reports or line listings):
	

 Serious Adverse Drug Reactions # of Reports Submitted: _____ Period from _____ to _____ DD/MMM/YYYY DD/MMM/YYYY
	

 Serious Adverse Events # of Reports Submitted: _____ (does NOT apply for marketed Amgen products) Period from _____ to _____ DD/MMM/YYYY DD/MMM/YYYY
	

Other Reports (to be sent as per contractual agreement eg, pregnancy/lactation reports)
	

 Specify type of report: _____ # of Reports Submitted: _____ Period from _____ to _____ DD/MMM/YYYY DD/MMM/YYYY
	

For multi-country studies please indicate countries of transmitted report(s) origin:
	

 
	

Total # of pages in this transmission, including cover page: _____
	

15.2 Sample of Report Form for Herpetic Event with Accidental Exposure of Close Contact or HCP to Talimogene Laherparepvec

AMGEN Study # XXXXXXX	Clinical Trial Report of Suspected Talimogene Laherparepvec Associated Adverse Event for HCP or Close Contact Notify Amgen Within 24 hours of awareness	 New  Follow-up
------------------------------------	--	--

SELECT OR TYPE IN A FAX#																												
SITE INFORMATION																												
Site Number	Investigator	Country																										
Reporter		Phone Number ()	Fax Number ()																									
INFORMATION FOR THE PERSON EXPERIENCING EVENT																												
Event ID	Associated Subject ID	Age at Time of Event ____ years	Gender  Male  Female	If female, is she currently pregnant?  Declined to provide  No  Yes (date of LMP) ____ / ____ / ____ (dd/mm/yyyy)																								
Indicate the relationship of the person experiencing the event with the associated (treated) subject																												
 Health care professional	 Close contact who is:  Residing with treated subject  Providing medical assistance/care to subject  Regularly in close contact with treated subject																											
1. Talimogene Laherparepvec administration to the treated subject (if known) 
 Date of first dose administration  ____ / ____ / ____ (dd/mm/yyyy) Date of last dose administration  ____ / ____ / ____ (dd/mm/yyyy)  Not applicable (e.g. exposure occurred during administration preparation) Product Lot Number: _____ or Unknown (✓): _____																												
2. History of person experiencing event 
 Previous history of herpes infections  No  Yes: Date of last episode ____ / ____ / ____ (dd/mm/yyyy) If the answer to a. above is YES, please complete: 
 
 Signs / Symptoms of herpes infections prior to known or suspected exposure to TVEC	Present	How many times per year?	
 
 Cold sores/fever blisters:  Oral  Genital			
 
 Othersuspected symptoms (describe):			
 
 
 Has the person ever been treated with antivirals, eg, acyclovir, for herpes infection?  No  Not sure  Yes (Date): ____ / ____ / ____ (dd/mm/yyyy) Method of treatment administration:  Topical  Oral  Intravenous Was the person taking any medications (other than antivirals addressed in 7c above) at the time of the event?  No  Not sure  Yes (Provide details below) 
  
 Medication	Indication	Start Date (dd/mm/yyyy)	Dose/Frequency	Continuing? If no, stop date (dd/mm/yyyy)	
   
 		____ / ____ / ____		 Yes  No ____ / ____ / ____	
 
 		____ / ____ / ____		 Yes  No ____ / ____ / ____	
  
					Signs / Symptoms of herpes infections prior to known or suspected exposure to TVEC	Present	How many times per year?	Cold sores/fever blisters:  Oral  Genital			Othersuspected symptoms (describe):			Medication	Indication	Start Date (dd/mm/yyyy)	Dose/Frequency	Continuing? If no, stop date (dd/mm/yyyy)			____ / ____ / ____		 Yes  No ____ / ____ / ____			____ / ____ / ____		 Yes  No ____ / ____ / ____
Signs / Symptoms of herpes infections prior to known or suspected exposure to TVEC	Present	How many times per year?																										
Cold sores/fever blisters:  Oral  Genital																												
Othersuspected symptoms (describe):																												
Medication	Indication	Start Date (dd/mm/yyyy)	Dose/Frequency	Continuing? If no, stop date (dd/mm/yyyy)																								
		____ / ____ / ____		 Yes  No ____ / ____ / ____																								
		____ / ____ / ____		 Yes  No ____ / ____ / ____																								

This form is subject to applicable laws governing the protection of personal information. The information provided on this form may be transferred and processed outside of the country in which it is collected. Do not provide any information by or through which a patient can be identified, other than the specific information required by the form. This prohibition includes, for example, name, address, telephone number and government issued identifier.

AMGEN Study # XXXXXXXX	Clinical Trial Report of Suspected Talmogene Laherparepvec Associated Adverse Event for HCP or Close Contact Notify Amgen Within 24 hours of awareness	 New  Follow-up
-------------------------------------	---	--

3. Details of each known or suspected exposure prior to this event

Exposure Information	Check all boxes that apply to known exposure(s)	
	Physical direct contact with treated patient	Caregiver
Date and Exposure ID ____ / ____ / ____ dd mm yyyy Exposure ID: ____ - ____ - ____  Date and Exposure ID not known	 Sleep together  Intimate physical contact (kissing, sexual intercourse)  Other (describe below):  Sleep together  Intimate physical contact (kissing, sexual intercourse)  Other (describe below):  Sleep together  Intimate physical contact (kissing, sexual intercourse)  Other (describe below):	 Dressing change  Injection site  Needle stick  Splash back  Other (describe below):  Dressing change  Injection site  Needle stick  Splash back  Other (describe below):  Dressing change  Injection site  Needle stick  Splash back  Other (describe below):
Date and Exposure ID ____ / ____ / ____ dd mm yyyy Exposure ID: ____ - ____ - ____  Date and Exposure ID not known	 Sleep together  Intimate physical contact (kissing, sexual intercourse)  Other (describe below):  Sleep together  Intimate physical contact (kissing, sexual intercourse)  Other (describe below):  Sleep together  Intimate physical contact (kissing, sexual intercourse)  Other (describe below):	 Dressing change  Injection site  Needle stick  Splash back  Other (describe below):  Dressing change  Injection site  Needle stick  Splash back  Other (describe below):  Dressing change  Injection site  Needle stick  Splash back  Other (describe below):
Date and Exposure ID ____ / ____ / ____ dd mm yyyy Exposure ID: ____ - ____ - ____  Date and Exposure ID not known	 Sleep together  Intimate physical contact (kissing, sexual intercourse)  Other (describe below):  Sleep together  Intimate physical contact (kissing, sexual intercourse)  Other (describe below):  Sleep together  Intimate physical contact (kissing, sexual intercourse)  Other (describe below):	 Dressing change  Injection site  Needle stick  Splash back  Other (describe below):  Dressing change  Injection site  Needle stick  Splash back  Other (describe below):  Dressing change  Injection site  Needle stick  Splash back  Other (describe below):

4. Evaluations, Diagnosis & Laboratory Measures

Diagnostic	Results/Units	Reference Range/Units	Date (dd/mm/yyyy)
Live virus assay			____ / ____ / ____
Quantitative Polymerase Chain Reaction (PCR)			____ / ____ / ____
Serologic test (antibody test)			____ / ____ / ____
Other (specify):			____ / ____ / ____
Other (specify):			____ / ____ / ____

This form is subject to applicable laws governing the protection of personal information. The information provided on this form may be transferred and processed outside of the country in which it is collected. Do not provide any information by or through which a patient can be identified, other than the specific information required by the form. This prohibition includes, for example, name, address, telephone number and government issued identifier.

AMGEN Study # XXXXXXX	Clinical Trial Report of Suspected Talmogene Laherparepvec Associated Adverse Event for HCP or Close Contact Notify Amgen Within 24 hours of awareness	 New  Follow-up
------------------------------------	---	--

5. Adverse Event Information:

a. Complete each row below for person experiencing herpetic signs and symptoms since the associated subject began treatment with Talmogene Laherparepvec. *Populate each row of the following table:*

Signs or Symptoms	Present?	Location on body	If Serious, enter Serious Criteria code (see codes below)	Relationship to TVEC	Date started (dd/mm/yyyy)	Date ended (dd/mm/yyyy)
Cold sores/fever blister, eg, on face, mouth, lip or nose single or multiple red papular or ulcerated lesions at muco-cutaneous junction, around mouth or on face, with pain, tingling or itching	 Yes  No			 Yes  No  unknown	____/____/____	____/____/____
Herpetic whitlow (painful, itchy blister lesion on fingertips of hand)	 Yes  No			 Yes  No  unknown	____/____/____	____/____/____
Cold sore/ fever blister in genital area	 Yes  No			 Yes  No  unknown	____/____/____	____/____/____
Herpes keratitis - eye signs and/or symptoms (redness, pain, photophobia (intolerance to light), blurred vision, tearing)	 Yes  No			 Yes  No  unknown	____/____/____	____/____/____
Herpes simplex encephalitis - neurological signs and/or symptoms (eg, fever associated with headache, vomiting, lethargy, psychiatric symptoms, seizures, weakness, confusion, or memory loss)	 Yes  No			 Yes  No  unknown	____/____/____	____/____/____
Other signs/symptoms: (DESCRIBE)	 Yes  No			 Yes  No  unknown	____/____/____	____/____/____
Serious Criteria:	01 Fatal 02 Immediately life-threatening 03 Required hospitalization 04 Prolonged hospitalization 05 Persistent or significant disability/incapacity 06 Congenital anomaly / birth defect 07 Other significant medical hazard					

b. Provide, if available, final diagnosis or syndrome: _____

AMGEN Study # XXXXXXXX	Clinical Trial Report of Suspected Talimogene Laherparepvec Associated Adverse Event for HCP or Close Contact Notify Amgen Within 24 hours of awareness	 New  Follow-up
-------------------------------------	--	--

6. Action Taken:

a. Did either of the following occur since the associated subject began treatment with Talimogene Laherparepvec?

Hospitalization No Yes: Date of hospitalization ____/____/____ (dd/mm/yyyy)

Consultation with other healthcare provider(s) No Yes: Date of consult(s)

Provide available hospitalization and consult reports with this document. Conceal personal identifiers and write the assigned Event ID number on reports. ____/____/____ (dd/mm/yyyy)
____/____/____ (dd/mm/yyyy)

b. Did the exposed/potentially exposed person receive treatment with antivirals, eg, acyclovir, for herpes infection?

No Not sure Yes (Date): ____/____/____ (dd/mm/yyyy)

Method of treatment administration: Topical Oral Intravenous

c. Did the person receive any other treatment?

No Not sure Yes (Provide details below)

Medication	Indication	Start Date (dd/mm/yyyy)	Dose/Frequency	Continuing? If no, stop date (dd/mm/yyyy)
		____/____/____		 Yes  No ____/____/____
		____/____/____		 Yes  No ____/____/____

d. Chronological summary of symptoms (narrative of events):

Signature of Investigator or Designee	Title	Date of report
---------------------------------------	-------	----------------

